**1.3.4. Exploratory Endpoints**

- Percent difference in pre-CPB vs. post-CPB blood ticagrelor active metabolite (TAM) levels as measured by LC/MS-MS
- Area under the concentration time curve (AUC), for intraoperative ticagrelor pharmacokinetic (PK) concentration and for TAM
- Operative time (i.e., duration of index operation, measured from start of skin incision to completion of chest closure)
- Duration of ICU stay
- Duration of hospital stay
- 30-day hospital readmissions

**1.3.5. Primary Safety Endpoint**

The primary safety endpoint of this trial is to evaluate the product safety profile through the GCP-level assessment of AEs during the study period.

**1.3.6. Additional Safety Endpoints:**

- 30-day cardiac mortality
- 30-day all-cause mortality
- 30-day postoperative stroke
- 30-day postoperative myocardial infarction (MI)
- Urgent postoperative coronary revascularization during the index hospitalization

- Serious device-related adverse events

### 1.3.7. Exploratory Subgroup Analyses

The primary effectiveness endpoint and its individual components will be analyzed in the following subgroups:

1. Surgical Characteristics
  - a. Procedure duration (skin incision to closure): <4 hours vs. 4-6 hours vs. >6 hours
  - b. CPB duration (i.e., device exposure):
    - Tertiles
    - Above and below median
2. Drug Removal
  - a. Time from Last Dose:
    1. Tertiles
    2. 0-24 vs. 24-48 vs. >48 hours
    3. above vs below median
    4. 0-24 vs. >24 hours
    5. 0-48 vs. >48 hours
  - b. Ticagrelor Levels
    6. Above vs. Below median pre-CPB levels (whole population)
    7. Above vs. Below median post-CPB levels (whole population)
    8. >67% vs. <67% removal (per intervention arm values)
    9. >50 vs. <50% removal (per intervention arm values)
    10. >40 vs. <40% removal (per intervention arm values)

The key secondary endpoint will be analyzed according to surgical characteristics and the time from last dose subgroups.

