3. STUDY JUSTIFICATION

Ticagrelor is the first FDA-approved, orally administered platelet inhibitor that reversibly antagonizes the P2Y₁₂ adenosine diphosphate (ADP) receptor on platelets. Ticagrelor is also recommended as part of dual anti-platelet therapy with aspirin, prior to percutaneous coronary intervention (PCI) and stent placement to reduce the risk of in-stent thrombosis. [1]

The most common adverse effect of ticagrelor is the increased risk of unwanted, serious, and potentially fatal bleeding from spontaneous events (e.g., gastrointestinal bleed, intracranial hemorrhagic stroke), major trauma, and/or unscheduled, emergent or urgent surgeries with high bleeding risk. Currently, there are no approved agents to either prevent or treat bleeding related to ticagrelor-induced platelet dysfunction. Held et. al. evaluated bleeding events in patients from the PLATO study who required CABG \leq 7 days of last ticagrelor dose (nearly 50% of which underwent surgery \leq 3 days since taking the drug). Within this population 81.3% experienced major bleeding events based on the PLATO study definitions; bleeding in accordance with the TIMI major criteria occurred in 59.3% of these patients, and 43.7% experienced CABG-related life threatening or fatal bleeding. [5] Most of the major bleeding events occurred within the first 24 hours after surgery. Data from the European Multicenter Registry on Coronary Artery Bypass Grafting (E-CABG) demonstrated that occurrence of major perioperative bleeding per Universal Definition of Perioperative Bleeding in Cardiac Surgery (UDPB) criteria was most significant in patients undergoing cardiac surgery \leq 2 days after last ticagrelor dose. [6] These patients experienced a 17.7% incidence of severe or massive bleeding by UDPB criteria, as compared to just 7.7% in patients waiting 3 days after last ticagrelor dose before undergoing surgery. With a propensity-score matched cohort the difference was 16.0% vs 2.7%, respectively (p = 0.003). [6] Of note, incidence of even *moderate* bleeding events is strongly influenced by timing of last ticagrelor dose prior to surgery. As seen within the CAPITAL Registry dataset, patients had a 40.5% incidence of *at least moderate* bleeding (UDPB \geq 2) when undergoing CABG $<$ 72hrs after last ticagrelor dose. This was compared to $<$ 20% incidence of such bleeding events in patients who were able to wait for longer wash-out periods. [14]

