Appendix 4: Schedule of Assessments**Table 5. Schedule of Antithrombotic and Anticoagulation Management**

Time period	Screening/ preoperative period	Operation	Postoperative day 1	>1 day post- operation	30-day follow- up	
Subjects with ACS or coronary stent placement within the previous 6 months						
Aspirin	X	X	X ^a	X	X	
Ticagrelor/P2Y ₁₂ inhibitor ^b	X ^c		X ^d	X	X	
Thromboprophylaxis		SOC ----- SOC				
All other subjects						
Aspirin	SOC	SOC	SOC	SOC	SOC	
Ticagrelor/P2Y ₁₂ inhibitor ^b	X ^c		SOC-----SOC			
Thromboprophylaxis		SOC ----- SOC				

^aSubjects not previously on Aspirin in the preoperative setting should be initiated on Aspirin therapy at 6 hours post-op, per institutional protocols

^bChoice of agent for postoperative DAPT is at the discretion of the treating physician, in accordance with standard clinical guidelines

^cTiming of last dose must be consistent with the study inclusion criteria

^dResumption of ticagrelor therapy should be within 24hrs post-op if there is no clinical concern for bleeding. Otherwise, if concern for bleeding exists, ticagrelor should be resumed as soon as deemed clinically safe in the judgement of the surgeon. Known benefit of ticagrelor in postoperative graft/stent patency must be weighed against bleeding risks

SOC = per institutional protocols

Table 6: Schedule of Assessments

Study Procedures	Screening	Pre-CPB	Operation	Post-CPB	Post-Operation					Follow-up Visit/End of Study/Early Termination	
Timepoint	Up to 2 days prior to the day of Operation	Within 2 hours before start of operation (i.e., skin incision)	From chest incision to chest closure	Within 30 min after end of CPB	ICU Admission	POD 1	POD 2	POD 3	POD 4	POD 5-29	POD 30 + 5 days
Informed consent/authorization ^a	X										
Inclusion/exclusion criteria	X										
Demographic information	X										
EuroScore II	X										
STS Risk Score	X										
Last pre-operation dose of ticagrelor (date, time, and dosage)	X										
Medication history within 30 days of study enrollment	X ^r										
Physical exam, height, weight ^b	X ^r										
Planned surgical procedure ^c	X										
Drug removal blood sampling ^d		X	X	X							
Medical history	X										
Concomitant medications	X	X	X		X	X	X	X	X	X ^s	X
EKG ^e	X				SOC ^t						
Pregnancy test ^f	X										
Cardiac troponin (cTn) ^g	X				SOC ^t						
Hematology ^g	X				X	X	X ^u	SOC	SOC	SOC	
Clinical chemistry ^g	X				X	X	X ^u	SOC	SOC	SOC	
Coagulation panel ^g	X				X	X	X ^u	SOC	SOC	SOC	

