## 2 SAMPLE SIZE AND STATISTICAL POWER CONSIDERATION

The hypothesis for the primary effectiveness endpoint will be tested using Finkelstein-Schoenfeld test (Finkelstein et al 1999). With the assumed effect sizes and variability for Scenario 1 outlined in Table 1 (Section 11.1 of the CIP), 57 subjects per arm will provide >99% power for the primary effectiveness endpoint based on Finkelstein-Schoenfeld test statistics at the two-sided significant level alpha ( $\alpha$ ) of 0.05. Taking into consideration higher than anticipated variability observed with the 24hr CTD variable, in scenario 2 we consider the same effect sizes in the 3 components and a larger variability (double of that in Scenario 1). In that instance the needed sample size is 65 per arm to achieve 92% power.

With this same sample size per arm, power for the key secondary endpoint is estimated >99.9%, and for 24-hour chest tube drainage (mL), >99.9%, based on a two-sample t-test assuming equal variance and a two-sided alpha of 0.05. Assuming unequal variances, power for comparisons of platelet transfusions (volume [mL]) and PRBC transfusions (volume [mL]), is estimated at 98.0% and 96.7%, respectively.

Allowing for ~7% dropouts, approximately 140 subjects will be randomized in a 1:1 ratio to the treatment and control arms to ensure that 130 subjects (65 per arm) will be evaluable for the primary effectiveness analysis.

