### 5.2.2.1 Significance Test

The primary hypothesis will be tested at the two-sided significance level of 0.05 using Finkelstein-Schoenfeld test statistics (Finkelstein et al 1999). All pairs of subjects are compared, regardless of the treatment groups, and a score  $W_{ij} = 1, -1$  or 0 is assigned to the pair  $(i, j)$  depending on whether subject i was a winner, a loser, or the comparison was inconclusive.

The test statistic is  $T = \sum_i D_i W_i$ , where  $D_i$  is the indicator variable for the treatment and  $W_i = \sum_j W_{ij}$ . Under the null distribution of no treatment effect, T is asymptotically normally distributed with mean 0 and variance  $\frac{n*m}{N*(N-1)} * \sum_i W_i^2$ , where n and m are the sample size for the treatment and control group respectively, and  $N = n + m$ .

Therefore, a significance test based on the standardized T statistic denoted by Z-statistics will be used to test the null hypothesis. The p-value will be provided and compared at the significance level of 0.05.

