##### **5.4.1.1 24-hour Chest Tube Drainage Volume**

24-hour CTD volume will be evaluated as the cumulative volume in CTD within 24 hours based on the observed data from the end of the index surgery. The subject with missing CTD volume within 24 hours due to death will be excluded from the analysis.

The ANCOVA model with treatment group and type of surgery (when deemed appropriate) as covariates will be employed to assess the treatment difference in 24-hour CTD. The p-

value and estimated mean difference along with the 95% CI will be provided between the treatment and control group.

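### Time from last ticagrelor dose is left out of the 24-hour CTD ANCOVA and examined only through five overlapping exploratory cuts with no lead analysis (minor)

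*SAP*

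**What the plan says.** Protocol section 3 argues that even moderate bleeding is "strongly influenced by timing of last ticagrelor dose prior to surgery". The Schedule of Assessments (Protocol Appendix 4, Table 6) has a screening row beginning "Last pre-operation dose of ticagrelor (date, time, and dosage".

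Randomisation is stratified by site and planned surgery type only (Protocol 6.1, SAP 3.3). The primary Finkelstein-Schoenfeld test has no strata or covariates: "All pairs of subjects are compared, regardless of the treatment groups" (SAP 5.2.2.1). The key secondary endpoint and the transfusion volumes use two-sample t-tests (SAP 5.3.1, 5.4.1.2). The CTD analysis, next in the fixed sequence after the key secondary, is the one alpha-controlled analysis with an explicit covariate model: an "ANCOVA model with treatment group and type of surgery (when deemed appropriate) as covariates" (SAP 5.4.1.1).

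Time from last dose appears as an analysis variable only in SAP 1.3.7, which is headed exploratory. It is cut five ways: tertiles; "0-24 vs. 24-48 vs. >48 hours"; above or below the median; split at 24 h; split at 48 h. The cuts apply to the primary endpoint, each of its components and the key secondary endpoint. The section names no test, no lead cut and no multiplicity rule. SAP 3.6 has a method for assessing consistency across subgroups, but its list does not include time from last dose.

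**The concern.** Two things look inefficient. First, the protocol treats time since the last dose as a main reason why these patients bleed and arranges to record it, but the one covariate model in the confirmatory sequence omits it. If time predicts drainage inside the eligibility window, adjusting for it narrows the CTD confidence interval at almost no cost. CTD also gates the secondary endpoints that follow it in the sequence.

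Second, five cuts of one variable with no lead analysis leave open which result is the effect-modification finding. The cuts overlap: the three-group cut contains both the 24 h and the 48 h boundaries. Eligibility is itself defined by time since the last dose, so a timing subgroup is a natural result to quote, and nothing in SAP 1.3.7 says which split would count.

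**Working it through.** **The plan's own power figures.** SAP section 2 states that "57 subjects per arm will provide >99% power for the primary effectiveness endpoint" (99.7% in SAP Table 1, CTD SD 253) and that, with the SD roughly doubled to 500, "the needed sample size is 65 per arm to achieve 92% power" (92.1% in Table 1). A 6,000-trial simulation of the SAP 5.2.2.1 statistic, with independent components and normal CTD, gave 99.5% and 91.8%. Both agree with the plan to within simulation error and modelling detail.

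For CTD alone, SAP section 2 states more than 99.9%. At SD 253 and 57 per arm the noncentrality is 320 / (253 × √(2/57)) = 6.75, which confirms it. At the Scenario 2 SD of 500 the figure is lower, and that is the baseline used below.

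**Precision of the CTD analysis.** Inputs from SAP Table 1, Scenario 2: means 480 and 800 mL (difference 320), SD 500, 65 per arm, two-sided 0.05. Let R² be the share of CTD variance that time from last dose explains. The documents give no value, so it is an assumption, shown from 0 to 20%.

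- Residual SD = 500 × √(1 − R²)
- Noncentrality = 320 / (residual SD × √(2/65))
- CI half-width = 1.96 × residual SD × √(2/65)
- Equivalent total sample = 130 / (1 − R²)

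| Assumed R² | Residual SD | Noncentrality | Power (t) | Half-width, mL | Equivalent N |
|---|---|---|---|---|---|
| 0 | 500.0 | 3.65 | 95.2% | 172 | 130 |
| 2% | 495.0 | 3.69 | 95.5% | 170 | 133 |
| 5% | 487.3 | 3.74 | 96.0% | 168 | 137 |
| 10% | 474.3 | 3.85 | 96.8% | 163 | 144 |
| 20% | 447.2 | 4.08 | 98.2% | 154 | 163 |

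A normal approximation gives values 0.1 to 0.3 points higher (95.4% at R² 0, 98.3% at 20%). At R² 0 the cost is one residual degree of freedom, 127 to 126 when surgery type is in the model. That does not move power at the precision shown.

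**What the documents say about R².** The gradients cited in Protocol 1.1 and 3 are:

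- a national registry: about 38% major bleeding at 24 h or less, against under 10% at 4-5 days;
- the pivotal ticagrelor trial: over 65% within 24 h, against 27.8% at 4-5 days;
- a European CABG registry: 17.7% severe or massive bleeding at two days or less, against 7.7% at three days;
- a further registry: 40.5% with UDPB class 2 or higher under 72 h, against under 20% with longer wash-out.

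The trial admits surgery within two days of the last treatment day (day 0) and excludes day 3 or later. These contrasts therefore mostly set eligible patients against patients with longer wash-out. None compares, say, 0-24 h with 24-48 h.

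**False interactions.** Null trials were simulated with 65 per arm, a continuous outcome and an F-test of treatment by subgroup at 0.05 for each of the five cuts. Each cut alone rejected in about 5% of trials. At least one of the five rejected in 13.2% (2,000 trials, time uniform on 0-72 h) and in 13.5% to 14.5% (6,000 trials for each of three assumed timing distributions on 6-72 h). Five independent tests would give 1 − 0.95⁵ = 22.6%; the overlap between cuts keeps the figure below that. One continuous interaction test gives 5%.

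**The case against.** The strongest reply is that the protocol's case for a strong timing effect concerns who is eligible, not variation among eligible patients. Restricting entry already deals with the documented contrast. This stands, and it is why the precision gain is unproven. It does not show that the gradient is zero. With the last treatment day as day 0, the interval can approach 72 h, the SAP itself provides a group beyond 48 h, and the registry contrast of 17.7% against 7.7% falls at the edge of the window.

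The second reply is that the 13-14% rests on a test that SAP 1.3.7 does not specify. The 0.05 interaction rule belongs to SAP 3.5 and is carried to the list in 3.6, where time from last dose does not appear. All five cuts are prespecified, so selective quotation would be visible. This also stands: the figure describes what would follow if each cut were tested, not a planned error rate.

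Third, Protocol 11.3 specifies a two-sample t-test for CTD, so another covariate moves the SAP further from it. True, but the SAP has already replaced that test with ANCOVA.

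Two practical points also stand. Scheduling the last-dose record does not guarantee that it is complete. And the interval to surgery ends after randomisation, although blinding of the surgical team makes an influence of allocation on the start time unlikely.

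A reader might infer that the omission biases the confirmatory comparisons or inflates their type I error. It does neither in a randomised trial. A reader might also want time added to the transfusion analyses, or the primary test stratified by it. The first would replace the t-tests that both documents specify. For the second, a simulated three-stratum version lost about 2 power points with no gradient (89.8% against 92.1%) and broke even only near R² 5%; as a supplementary analysis it would change no conclusion. The documents do not support pressing either.

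**Conclusion.** The point holds as a minor one. Time from last dose is missing from the CTD ANCOVA, and its exploratory treatment has no lead analysis. Adjustment would raise CTD power by about 0.3 points at R² 2% and 3 points at 20%, from 95%. These figures assume SD 500, a 320 mL difference, 65 per arm and R² values that the documents neither give nor rule out. The cut-point issue affects how an exploratory result is read: about 13-14% against 5% per endpoint, if each cut were tested at 0.05. Trial type I error is unaffected, and the primary, key secondary and transfusion analyses need no change on this account. A claim that substantial precision is being lost would go beyond the evidence.

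**What to change.** Before unblinding, amend the SAP in two places.

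- **5.4.1.1:** add time from last ticagrelor dose to start of surgery (hours, continuous) as a prespecified covariate alongside surgery type. Define the end point of the interval and say how a missing last-dose time is handled.
- **1.3.7:** test effect modification by time from last dose once per endpoint, as treatment by continuous time. Keep 0-24, 24-48 and over 48 h as the single display grouping. Drop the tertile, median, 24 h and 48 h cuts, or label them descriptive.

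The cost is SAP wording, one residual degree of freedom, and a further small departure from the protocol's t-test for CTD, which should be recorded as such. No new data are needed, and there would be fewer tables if the extra cuts go.

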1.5. Study Design

The STAR-T study is designed to demonstrate reductions in postoperative bleeding complications with the intraoperative use of DrugSorb™-ATR in patients undergoing cardiothoracic surgery within two days of ticagrelor discontinuation. These patients have been demonstrated in the literature to be at

greatest risk for bleeding complications (refer to **Section 3** for details). The study also aims to establish the safety of intraoperative DrugSorb™-ATR use in the target population.

The mechanism of action is removal of ticagrelor from active circulation through hemoadsorption while the patient is on cardiopulmonary bypass. Thus, the change in total blood concentration of ticagrelor following CPB will be measured as a key secondary endpoint. To do so, patient blood samples will be obtained during the pre-operative and immediate post-CPB time periods for ticagrelor concentration testing. This will allow comparison of clinical outcomes with presence or absence of reduction in circulating drug concentration. Serial sampling (every 30 min) for quantification of serial changes in blood ticagrelor levels will also be obtained through the first 2 hours of therapy on CPB. This supplemental drug removal data will be analyzed as an exploratory endpoint. Additional outcome measures to be evaluated include those that are documented as part of routine care, and are detailed in **Section 4.3**.

[figure not shown]

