5.2. Potential Benefits

The observed and potential benefits of using the DrugSorb™-ATR device intra-operatively during cardiothoracic surgery to remove ticagrelor include:

- Decrease in perioperative bleeding complications; including:
 - Decrease in perioperative blood loss, including that measured in chest/mediastinal drains
 - Decrease in blood product transfusions
 - Reduced risk of re-operation for bleeding
 - Reduced risk of fatal bleeding
- Improvement in hemodynamic stability and reduction in vasopressor requirements
- Decrease in mean operative time including time to hemostasis
- Decrease in the amount of time on a mechanical ventilator
- Decrease in hospital stay following surgery, including time in the ICU

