11.4. Subgroup Analysis

The primary effectiveness endpoint will also be analyzed across the clinically meaningful subgroups, including but not limited to those outlined below:

- Planned surgery type (CABG alone vs. all other types of surgery)
- Key demographic factors including age (<65 vs. ≥ 65 years old) and sex (M/F)
- EuroScore II score
- STS Risk score (low, intermediate, high)
- NYHA heart failure class (1, 2, 3, 4)
- Left ventricular ejection fraction [according to the ACC classification: $\geq 50\%$ (normal), 40-49% (mild dysfunction), 30-39% (moderate dysfunction), <30% (severe dysfunction)]
- Baseline thrombocytopenia (platelet count $< 150,000 \mu/L$, $\geq 150,000 \mu/L$)
- Prior MI (Y/N)
- Prior stroke (Y/N)
- Prior hypertension (Y/N)
- Prior hyperlipidemia (Y/N)
- Diabetes mellitus (Y/N)
- Chronic obstructive pulmonary disease/COPD (Y/N)
- Current or prior tobacco use (Y/N)
- Prior sternotomy (Y/N)
- Drug removal

Additional details on subgroup analyses will be provided in the SAP.

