### 3.6 Homogeneity Across Subgroups of Interest

The following analysis will be carried out on the mITT, PP, i-CABG mITT, and i-CABG PP populations with no imputation for missing data.

Appropriate descriptive statistics of the primary effectiveness endpoint and its components will be presented by treatment group (treatment vs control) within the subgroup categories below. The purpose of this analysis is not to assess significance of the treatment effect (treatment vs. control on the primary effectiveness endpoint and its components) within subgroups but to assess consistency of treatment effect on the primary effectiveness endpoint and its components across subgroups.

The following is a list of the subgroups to be investigated. For each subgrouping, in order to assess homogeneity of treatment effect on the primary effectiveness endpoint and its components, assessment of treatment-by-subgroup category interaction will be carried out in a similar manner as discussed previously for assessing homogeneity across regions.

We will evaluate the consistency of effectiveness on the primary effectiveness endpoint and its components (homogeneity), in the following subgroups:

1. Sex: Male vs Female
2. Age: <65 vs.  $\geq 65$
3. CABG vs. other procedures
4. Pre-existing clinical risk factors
  - a. EuroScore II <7%;  $\geq 7\%$ )
  - b. STS mortality risk score (<4% [low], 4%-8% [intermediate], >8% [high])
  - c. Baseline thrombocytopenia (platelet count <150,000  $\mu\text{L}$  vs.  $\geq 150,000 \mu\text{L}$ )

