### **5.2.2.2 Win Ratio Estimates**

In order to evaluate the magnitude of treatment effect in the primary effectiveness endpoint, the unmatched win ratio estimates (Pocock 2012) will be provided as well as the corresponding 95% confidence interval (CI).

The unmatched win ratios are formed by comparing every subject in the treatment group with every subject in the control group. Specifically, if we let  $n, m$  be the number of subjects in the treatment and control groups, respectively, then we make  $n \times m$  paired comparisons. The win ratio is then calculated as  $N_W/N_L$  where  $N_W$  and  $N_L$  are the total number of pairwise wins and losses, respectively, for the treatment group.

Following Bebu (2016), logarithm of  $\widehat{WR} = N_W/N_L$  has an asymptotic normal distribution with mean and variance specified in (2.6) of the paper. Therefore, the estimated WR and the 95% Confidence Interval (CI) will also be derived and presented from the sample distribution of  $\log(\widehat{WR})$  using Delta method with the exponential transformation.

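### SAP 1.3.7 item 7 analyses the primary endpoint within halves of the post-CPB ticagrelor level, which the device is meant to lower, so arm contrasts there are not randomised comparisons (minor)

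*SAP*

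**What the plan says.** SAP 1.3.7, headed as exploratory, opens with "The primary effectiveness endpoint and its individual components will be analyzed in the following subgroups". Under Drug Removal it numbers ten splits. Items 1-5 are cuts of time from last dose. Item 6 is the median pre-CPB level. Item 7 is "Above vs. Below median post-CPB levels (whole population"). Items 8-10 are cuts of percent removal, the first being ">67% vs. <67% removal (per intervention arm values").

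The section names no method. The effect measure for the primary endpoint is given in SAP 5.2.2.2: "The unmatched win ratios are formed by comparing every subject in the treatment group with every subject in the control group".

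Protocol 11.3 expects a 40% reduction (SD 40%) in the device arm and minimal change in control. SAP A 1.1.1 places the post-CPB sample after bypass has ended, so after device exposure. Protocol 11.4 ends its list of subgroups for the primary endpoint with drug removal and adds "Additional details on subgroup analyses will be provided in the SAP".

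**The concern.** A subgroup contrast between arms keeps the protection of randomisation only if the grouping variable could not have been altered by the treatment. Post-CPB level is what the device is built to alter, and its percent change is the key secondary endpoint. A control in the low half mostly got there by starting with little drug. A device patient may have got there by starting with a lot and having it removed. The arms within a half then differ in starting level before any effect on bleeding is considered.

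Protocol Section 3 wants the drug-removal data to link removal with less bleeding. Item 7 looks like evidence on that link, but it can hide part of a true benefit or, in another setting, suggest a small disadvantage that is not there. SAP 3.6 carries a caution, "The purpose of this analysis is not to assess significance of the treatment effect", but that section governs its own list (sex, age, procedure, risk scores, platelets), which does not include post-CPB level.

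**Working it through.** **Inputs from the documents.** Removal 40% (SD 40%) on device and about 0 in control (Protocol 11.3). 65 evaluable per arm (SAP 2). Control planning values: fatal bleeding 3.0%, UDPB class 2 or higher 40.5%, CTD 800 mL with SD 253 or 500 (SAP Table 1).

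**Assumed, because not given.** Pre-CPB level lognormal with CV 50% or 100%; SD of control change 20% or 40%; strength of the link between drug level and bleeding.

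**1. The plan's own figure.** Key secondary power, with d = 40/40 = 1, is about Φ(d√(n/2) − 1.96). For n = 57: Φ(5.34 − 1.96) = 99.96%. For n = 65: Φ(5.70 − 1.96) = 99.99%. The stated figure of >99.9% is reproduced. The same assumption implies that the arms separate on the variable used in item 7.

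**2. Composition of the halves by hand, removal fixed at 40%.** On the log scale σ² = ln(1 + CV²), so σ = 0.472 (CV 50%) or 0.833 (CV 100%). The device arm shifts by ln 0.6 = −0.511, so the pooled post-CPB median lies halfway, at −0.255 relative to the pre-CPB median.

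- To fall in the low half, a control must have started below e^(−0.255) = 0.77 times the median pre-CPB level. A device patient may have started as high as e^(0.255) = 1.29 times it.
- Device share of the low half = Φ(0.255/σ) = Φ(0.541) = 71% or Φ(0.307) = 62%.
- Ratio of geometric mean pre-CPB level, device to control, with z = 0.255/σ: exp{σ[φ(z)/(1 − Φ(z)) − φ(z)/Φ(z)]} = 1.38 at either CV.

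**3. Composition with variable removal (simulation).** With device SD 40% and control SD 20-40%, the device share of the low half is 61-67%, or about 40-44 of 65 patients. Device patients there have a geometric mean pre-CPB level 1.19-1.53 times that of the controls. These results need no assumption about bleeding.

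**4. Win ratios (simulation).** Each component is tied to log drug level with strength r, and components share half their residual variance. Ranges run over the CV and control-SD combinations and pool separate runs.

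| Setting | Overall | Post-CPB low half | Post-CPB high half | Pre-CPB halves (item 6) |
|---|---|---|---|---|
| No device effect, r = 0 | about 1 | 1.00-1.01 | 0.99-1.00 | about 1 |
| No device effect, pre-CPB level acts directly, r = 0.2 | about 1.00 | 0.85-0.93 | 0.94-0.97 | 0.99-1.01 |
| Bleeding acts through post-CPB level, 0.2 per SD | 1.20-1.48 | 1.18-1.46 | 1.02-1.07 | 1.24-1.50 |

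The last pre-CPB entry comes from the run whose overall range was 1.24-1.48.

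In the third row the high half loses nearly all the benefit. The low half is attenuated little or inconsistently: in a further run with CV 50% and control SD 10% it gave 1.56 against 1.52 overall. Item 6 recovers the overall effect in both of the lower rows.

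**5. Size against noise, second row.** Rejection at nominal 5% is 6.5-8.6% in the low half and 4.6-5.3% in the high half. The SD of the log win ratio within a half is about 0.30. The shifts are ln 0.85 = −0.163 and ln 0.93 = −0.073, or 0.54 and 0.24 of that SD. A 95% interval spans a factor of e^(1.96 × 0.30) = 1.8 either way. The spurious CTD difference in the low half is 0.073-0.123 SD: 18-31 mL at SD 253, or 37-62 mL at SD 500.

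**The case against.** The strongest reply has four parts.

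- **Direction.** A reader might infer that item 7 leans against the device whenever pre-CPB level predicts bleeding. The documents do not support that. Protocol Section 3 says platelet activity follows the plasma level closely because receptor kinetics are rapid. Blood-product transfusions and chest drainage count towards UDPB only from chest closure, which comes after bypass. Both points favour the setting in which bleeding acts through post-CPB level, and there neither half reverses. A false disadvantage needs a path that bypasses post-CPB level, and no passage gives one. This part stands, so the main distortion is loss of benefit in the high half.
- **Size.** At planned removal the false disadvantage is about half a standard error or less. It grows with removal: at an assumed 60% (SD 20%) the halves are 0.79-0.89 and 0.84-0.88. The documents plan on 40%, and the 80% figure in Protocol 1.2 is a bench result. This part also stands.
- **Reading.** SAP 1.3.7 states no method, and Protocol 1.5 says of the drug samples "This will allow comparison of clinical outcomes with presence or absence of reduction in circulating drug concentration". Outcomes above and below the median could therefore be compared without contrasting arms. That is possible, but for a win-ratio endpoint the arm contrast is the more natural reading and nothing excludes it.
- **Status.** The analysis is exploratory. That limits the harm but does not make the contrast interpretable.

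A reader might also conclude that items 8-10 are wrong. They are unclear. The qualifier about intervention-arm values could mean that both arms are split, that device subsets are set against all controls, or that high and low removers are compared within the device arm. The first two share the defect of item 7. The third is an ordinary exposure-response look.

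**Conclusion.** The concern holds in limited form. As an arm contrast, item 7 conditions on a post-randomisation variable that the device changes by design, and the arms within each half are unequal in size and in starting drug level under the plan's removal figures and the assumed spreads.

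If the protocol's premise is right, the high half hides most of a real benefit (about 1.02-1.07 against 1.20-1.48 overall). If pre-CPB level acts by a separate path, both halves lean modestly against the device with no true effect. If drug level and bleeding are unrelated, there is no bias.

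The pre-CPB CV, the control SD and the coefficient of 0.2 are assumptions, so the win ratios are illustrative. The primary test, the overall comparison and the fixed testing sequence are untouched, and nothing here supports doubting them. Severity is minor.

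**What to change.** In SAP 1.3.7:

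1. Do not present item 7 as a between-arm effect. Drop it, or report it descriptively and label it post-randomisation and non-randomised.
2. Use the pre-CPB median (item 6) and time from last dose (items 1-5) for arm contrasts. Both are fixed before the device runs.
3. Optionally, state that items 8-10 compare patients within the device arm. If both arms were split at 67%, the expected numbers above the cut would be 65 × [1 − Φ((67 − 40)/40)] = 16 device patients against 0-3 controls (control SD 20-40%).
4. Optionally, supplement items 8-10 with a device-arm regression of 24-hour CTD on percent removal, adjusted for pre-CPB level and planned surgery type and labelled as association. Adjust for CPB duration only as a sensitivity analysis, because SAP 1.3.7 equates it with device exposure. The regression should not replace items 8-10, since Protocol 11.4 commits to analysing the primary endpoint by drug removal.

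The cost is a few sentences of SAP text, a little programming if step 4 is taken, and one exploratory between-arm table. No new data are needed, and no protocol amendment, because Protocol 11.4 leaves the subgroup details to the SAP.
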